5.3.1 COMPENSATION

Subject to approval by the IRB, subjects returning for neurodevelopmental testing and, in a subset, brain MRI, will receive \$100 for the subject and, if MRI is done, the subject (or parent/guardian as applicable) will receive a composite set of MPGR MRI images of the subject's brain if desired. Subject (or parent/guardian as applicable) will also receive the results of their neurodevelopmental testing, and in the subset who undergo brain MRI, results of neuroimaging. Reimbursement for travel expenses incurred due to study participation will be provided to all participants including, but not limited to, parking, mileage, ground transportation, and meals. In addition, for subjects traveling from afar, reimbursement for hotel and transportation (e.g. airfare, train) will be provided to participants in accordance with guidelines set by the ACC.

5.4 SUBJECT WITHDRAWAL OR TERMINATION

5.4.1 REASONS FOR WITHDRAWAL OR TERMINATION

Subjects may withdraw from participation in the study at any time.

An investigator may terminate participation in the study for the following reasons, including but not limited to:

- Any condition or abnormality that develops such that continued participation in the study would not be in the best interest of the subject
- The subject meets an exclusion criterion (either newly developed or not previously recognized) that precludes further study participation
- The subject is unable and/or unwilling to complete the study visits/procedures

5.4.2 HANDLING OF SUBJECT WITHDRAWALS OR TERMINATION

Data from subjects who withdraw or are terminated from the study will remain in the database unless the subject specifies in writing to the Investigator that they wish for their data to be removed. No other special procedures are required for subject withdrawals or terminations.

5.5 PREMATURE TERMINATION OR SUSPENSION OF STUDY

This study may be temporarily suspended or prematurely terminated if there is sufficient reasonable cause. Written notification, documenting the reason for the study suspension or termination, will be provided by the suspending or terminating party to the investigator, funding agency, and sponsor. If the study is prematurely terminated or suspended, the PI will promptly inform the IRB and will provide the reason(s) for the termination or suspension.

The study may resume once concerns about the study that led to suspension (e.g. safety, protocol compliance, data quality) are addressed and satisfy the Sponsor, funding agency, and the IRB.

6 STUDY AGENT

This is an observational study. No study agent is used.

7 STUDY PROCEDURES AND SCHEDULE

7.1 STUDY PROCEDURES/EVALUATIONS

7.1.1 STUDY SPECIFIC PROCEDURES

A subject will be considered enrolled following documentation of informed consent.

Following informed consent (as outlined in section 13.3) the following procedures will be performed as part of the study and should occur within 6 months of the first in-person evaluation:

- Demographic, medical history, concomitant medication and clinical characteristics data collection
- Neurocognitive and Behavioral Health Evaluation
- Brain MRI Imaging, in a subset of enrolled subjects

Data Collection

- Review of Inclusion/Exclusion criteria
- Medical history will be obtained by interview with the subject/parent/legal guardian as well as review of the medical chart. Medical history will include collection of WES or WGS results and other relevant data from the CHD GENES database, where available.
- Measurement of subject height and weight
- Concomitant Medication Review
- Collection of primary care physician name (if subject consents for results to be shared)

Brain MRI Imaging

- Brain MRI imaging will be performed in a subset of subjects, i.e., those enrolled at selected centers who have no contraindications to having brain MRI.
- Brain MRI imaging without contrast or sedation will be performed.
- Institutional policy for pregnancy testing prior to research MRI will be followed.
- Details of the brain MRI imaging parameters will be defined in the study specific Manual of Operations. The following MRI sequences will be performed:
 - Structural MRI
 - Diffusion Tensor MRI
 - Resting State Functional MRI
- Subjects unable or unwilling to have the brain MRI imaging may still be enrolled into the study to collect neurocognitive and behavioral health endpoints.

Neurocognitive and Behavioral Health Evaluation

- Neurodevelopmental assessment of the subject will be performed by a licensed psychologist or supervised psychometrician at each site according to Table 5 below. Multiple areas will be assessed including intellectual functioning, academic (reading and math) functioning, language, memory, attention/executive functioning, visual spatial, fine motor, social functioning, adaptive skills, emotional/behavioral functioning, and quality of life.
- Standardization and Certification: The evaluators (licensed psychologist and/or supervised psychometrician) at each site will complete a certification process to optimize standardization of the testing battery. If the testing is performed by someone other than a licensed psychologist, a licensed psychologist at the site will be expected to provide training and oversight for the individuals performing the evaluation. For all evaluators, a recording of the evaluator performing the test battery on a staff volunteer will be submitted for review by the co-chairs of the neurocognitive and behavioral health testing protocol. The certification videos can be in any format and sent on any medium (jump drive, SD card, DVD) as long as the file can be opened and reviewed. Any concerns related to the performance of testing will be relayed back to the site licensed psychologist and to the individual performing the testing. Upon review of the

administration video and test protocols, a feedback form that includes a pass/fail decision will be provided to the ACC for inclusion in the trial master file. A follow-up video and test protocol submission will be necessary if an evaluator fails the certification process.

7.1.1.1 Developmental Assessments and Testing

Parent, Participant, and Teacher Report Instruments - Questionnaires to be completed by the parent/caregiver are listed in Tables 1 and 2. Questionnaires to be completed by the participant are listed in Table 3. Teacher Reports are listed in Table 4. After consent has been obtained, the parent and teacher response instruments (per the tables below) may be mailed to the parents prior to the scheduled ND testing of their child along with a cover letter explaining the process for completing the instruments. Parent/caregiver will be instructed to pick the teacher whom they feel knows their child best to complete the teacher instruments. Consent for teacher completion of the instruments will be implied based on the teacher completing the instrument. Parent/caregiver instruments may be completed either before or during the child's evaluation as per the tables below. If completed before, completion must be within 3 months of the in-person evaluation and within 6 months of the MRI. (See details of consent described in section 13.3.2 for consent procedure prior to completing forms at home.)

The parent/caregiver questionnaires will require approximately 1-2 hours to complete. Teacher questionnaires will require approximately 40 minutes to complete.

Table 1 – Questionnaires Generally Completed by the Parent/Caregiver Prior to Study Visit*		
Measure	Age Range	Time to Administer
Social Responsiveness Scale, 2 nd Edition (SRS-2)	≥ 8 yrs	15-20 min

*May be mailed to parent/caregiver and completed prior to study visit. If mailed, participants will be phone consented following procedures in section 13.3.2. The purpose of SRS completion prior to the site visit is to facilitate the scheduling of the ADOS during the in-person visit. However, the SRS can also be completed at the time of the visit.

The version of the SRS-2 that will be completed will depend on the age and independent functioning of the participants as follows: For participants <18 years of age, parent/caregiver will complete the SRS-2 School-age form. Parent/caregiver (or legally appointed representative, if applicable) of all participants ≥ 18 years old will be asked to complete the SRS-2 Adult (Relative/Other) Form. For participants ≥ 18 years old, the coordinator will obtain the name/address of the designated parent/caregiver from the study subject and mail the questionnaire, with a self-addressed return envelope.

Measure	Age Range	Time to Administer
BASC-3 Parent Report	< 22 yrs	10-20 min
BRIEF-2 Parent Report	< 18 yrs	20 min
Children's Depression Inventory, 2 nd Edition (CDI-2)	< 18 yrs	5 min
Conners-3 Parent Report	< 18 yrs	20 min
MASC-2 Parent Report	< 18 yrs	5 min
Peds QL Parent Report (generic and cardiac modules)	< 18 yrs	10 min
Vineland-3 Caregiver Rating Form	≥ 8 yrs	20-60 min

*May be mailed to parent/caregiver and completed prior to study visit. If mailed, participants will be phone consented following procedures in section 13.3.2. Also, if the parent/caregiver is primarily Spanish-speaking and/or indicates they are unable to read English fluently, the Spanish version of the questionnaires will be administered when available.

The version of the BASC-3 that will be completed will depend on the age and independent functioning of the participants as follows: For participants ages 8-11 years of age, parent/caregiver will complete the BASC-3 Child Form. For participants ages 12 to < 22 years (i.e., through 21 years, 11 months), parent/caregiver or the LAR will complete the Adolescent form. The coordinator will determine which form to send based on the age of the participant.

The Vineland-3 Caregiver Rating Form is a survey form which must be filled out by the parent/caregiver for participants ages 8 and up.

Measure	Age Range	Time to Administer
Beck Anxiety Inventory	≥ 18 yrs	5 – 10 min
Beck Depression Inventory, 2 nd Edition (BDI-2)	≥ 18 yrs	5 min
CAARS Self-Report (CAARS-S)	≥ 18 yrs	20 min
Peds QL (generic and cardiac modules)*	< 18 yrs	10 min
QOLS*	≥ 18 yrs	5 min

*May be mailed and completed prior to study visit. If mailed, participants will be phone consented following procedures in section 13.3.2. If participant is primarily Spanish-speaking and/or indicates s/he is unable to read English fluently, the Spanish version of the questionnaires will be administered when available.

Measure	Age Range	Time to Administer
Conners-3	< 18 yrs	20 min
BRIEF-2	< 18 yrs	20 min

Direct testing battery - The direct testing evaluation will require approximately 3.5 hours of in-person testing without the autism tests, and approximately 4.5 hours with autism testing. Breaks will be provided for snacks/lunch and in response to the level of fatigue displayed, as appropriate for the

subject. Whenever possible, the in-person battery will begin in the morning as the first activity for the subject. Following the visit, parents/guardians will be sent a summary of their child's test results, if requested, that will be scored based on age-based norms after all ND and MRI testing has been completed for the subject. In-person tests will be administered in the order specified in Table 5 whenever possible. Additional information regarding the testing is provided in the CHD Brain and Genes Neurodevelopmental (ND) Testing MOO.

Table 5 – Battery of ND Tests to be Administered in Sequential Order During Study Visit			
Order	Measure	Age Range	Time to Administer*
1	VMI-6	≥ 8 yrs	5 min
2	WISC-V - Core Subtests: 
 • Similarities • Vocabulary • Block Design • Matrix Reasoning • Figure Weights • Digit Span • Coding • Symbol Search 	< 16 yrs	60 min
3	WAIS-IV - Core Subtests: 
 • Block Design • Similarities • Digit Span • Matrix Reasoning • Vocabulary • Arithmetic • Symbol Search • Visual Puzzles • Information • Coding 	≥ 16 yrs	60-90 min
4	WRAML-2 Story Memory & Picture Memory Immediate Recall Tasks	≥8 yrs	20 min
5	WRAT-4 Word Reading	≥8 yrs	35-45 min (total for all subtests)
6	WRAML-2 Story Memory & Delayed Recognition Recall Tasks	≥8 yrs	20 min
7	WRAT-4 Remaining Subtests 
 • Sentence Comprehension • Spelling • Math Computation 	≥8 yrs	35-45 min (total for all subtests)
8	D-KEFS (Selected Subtests) 
 • Verbal Fluency • Trail Making • Tower Subtests 	≥ 8 yrs	20 min
9	WIAT-III 
 • Listening Comprehension • Oral Expression Subtests Only 	≥ 8 yrs	14 min 19 min

10	Reading the Mind in the Eyes Task 
 • Child Version • Adult Version 	< 18 yrs ≥ 18 yrs	15 – 18 min 15 – 18 min
11	Questionnaire Measures for Older Participants: 
 • BDI-2 • BAI • CAARS 	≥ 18 yrs ≥ 18 yrs ≥ 18 yrs	5 min 5 min 20 min
12	ADOS-2**	≥ 8 yrs	40-60 min + scoring time

*'Time to Administer' in Tables 1-5 above are approximations.

**The ADOS-2 will be administered if the SRS-2 Total Score ≥ 60 or if the coordinator, in his or her best judgment and after consulting with the research site's psychologist, believes that there is a strong likelihood of an Autism Spectrum Disorder despite the absence of an elevation ≥ 60 on the SRS-2. This determination will be made in consideration of the current DSM-V diagnostic criteria for Autism Spectrum Disorder. That is, if the SRS-2 is < 60 but it is apparent from discussion with the parent/caregiver that there appears to be a strong likelihood of persistent deficits in social communication and social interactions in addition to the indication of restricted, repetitive patterns of behavior, interests, or activities. If such a determination is made, it will be discussed with the site PI for final confirmation.

Counseling procedures – If the subject/parent exhibits undue stress or signs of suicidal ideation during the neurodevelopmental testing, counseling will be provided.

7.1.1.2 Methods for MRI Testing.

Subjects with certain types of metal implants, such as surgical clips or pacemakers, will not have an MRI scan due to the use of powerful magnets to make images. During the scanning session, each patient will wear protective earphones, which will reduce the noise heard from the scanner. Audio-video entertainment with headphones may be provided to the subjects during the MRI sessions except during the resting state fMRI acquisition when the entertainment system will be deactivated. If a subject indicates that they are experiencing discomfort from lying in the confined space of the scanner and does not wish to continue, the scanning will be stopped immediately. No sedation will be used for brain MRIs that are performed for research purposes only. Prior to conducting the study scan, participants may undergo acclimation procedures, as described in the CHD Brain and Genes MRI MOO.

MRI scan staff will use all available tools at their disposal to make the scanning experience comfortable and the scans acceptable. Examples of comfort measures that may be used by centers include: form-fitting pillows, a magnet compatible sound system, protective earphones, a parent in attendance, and a two-way intercom. An attendant must remain at the bore and remain at the scanner until the proband is helped out of the scan room.

Subjects who cannot undergo this test without sedation will not be included in the MRI portion of this protocol. Subjects who decline to undergo MRI may still be enrolled in the study and will complete the neurodevelopmental assessments and data collection aspects of the protocol only.

The scanners used to acquire the brain MRIs will be calibrated and harmonized across sites during study start-up. The specific calibration and image acquisition process will be contained within the CHD Brain and Genes MRI MOO that each site will receive prior to enrolling their first subject. Training for site MRI staff will be described in the CHD Brain and Genes MRI MOO.

MRI variables

Specific sequences will allow derivation of a variety of brain MRI measures. The most important major categories of MRI outcomes are derived from the following core MRI sequences:

1. Structural MRI
2. Diffusion Tensor MRI
3. Resting State Functional MRI

Measured and derived parameters to be recorded include, but may not be limited to, the following:

1. Volume and image intensity (i.e. T1-weighted, T2-weighted) measures for subcortical volumes.
2. Surface-based morphometry measures (e.g. thickness, area) and image intensity measures (i.e. T1-weighted, T2-weighted) for cortical surface parcellations
3. Diffusion derived measures (e.g. fractional anisotropy (FA) and mean diffusivity (MD)) for white matter tracts, subcortical regions, and cortical surface parcellations
4. Resting state network connectivity measures

The specific methods and sequences for each of these domains will be specified by the PCGC Imaging Working Group (IWG) that will contain representative(s) from the MRI Core Lab and will be included in the MRI MOO.

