3 OBJECTIVES AND PURPOSE

1. Aim 1: To compare neurodevelopmental and behavioral health outcomes in individuals with CHD who have deleterious mutations (damaging de novo mutations or stringently defined deleterious missense mutations) on whole exome sequencing (WES) or whole genome sequencing (WGS) vs. those without such variants. Patients with stringently defined pathogenic CNVs or mutations in previously established CHD genes will be excluded from the study.

We will compare groups with respect to achievement, IQ, learning disability, specific neuropsychological domains (e.g., memory, attention, executive functions, and visual-spatial/motor integration), adaptive function, behavior, social cognition and symptoms of autism spectrum disorder, and quality of life. The primary study outcome for this aim will be the WRAT4 composite score.

2. Aim 2: To compare abnormalities in brain structure and microstructure on MRI in individuals with CHD who have deleterious mutations on WES or WGS vs. those without any deleterious variants. Neither group will have stringently defined pathogenic CNVs or mutations in previously established CHD genes.

We will compare the groups with respect to measured and derived parameters including, but not limited to, 1) regional volumetric and cortical thickness, 2) regional surface metrics, 3) voxel-based DTI eigenvectors and apparent diffusion coefficient (ADC) values, and resting state principal component analysis.

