4.1.2 SECONDARY ENDPOINTS

Secondary neurodevelopmental outcomes using age appropriate instruments will include the following:

- Visual spatial skill (VMI-6)
- Intelligence (WISC-V or WAIS-IV)
- Memory (WRAML-2 story memory subtest)
- Memory (WRAML-2 picture memory subtest)
- Executive function (D-KEFS verbal fluency, trail making subtext, and tower subtest)
- Language (WIAT-III oral language composite score) (listening comprehension and oral expression)
- Social cognition (Reading the mind in the eyes)

Secondary neurodevelopmental outcomes for probands assessed for autism include the following:

- ADOS-2

Brain structure/microstructure outcomes including but not limited to the following:

- Regional volumetric and cortical thickness measures
- Regional surface metrics
- Voxel-based DTI eigenvectors and apparent diffusion coefficient (ADC) values
- Resting state principal components

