10 STATISTICAL CONSIDERATIONS

10.1 STATISTICAL HYPOTHESES

We hypothesize that patients with deleterious mutations will have more neurodevelopmental abnormalities than CHD patients without these mutations. In exploratory analyses with limited statistical power, we expect to see the greatest developmental deficits in subjects with deleterious mutations in loss of function genes that are expressed in both the heart and brain. We also hypothesize that there will be worse outcomes in patients with independent deleterious mutations in heart and brain, as well as in those with either deleterious mutations or unfavorable polymorphisms in neuroresilience genes.

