The primary analysis for all endpoints (primary and secondary) will compare patients with and without known deleterious mutations and will include the matching factors of site, CHD type, sex, and age category using a generalized analysis of variance model. Because socioeconomic status (SES) has a proven effect on neurodevelopmental performance in virtually all published studies, we will also adjust for this variable in all models. An appropriate link and distribution function will be used depending on the distribution of the outcome variable (e.g. identity link and normal distribution for normal data, logit link and binomial distribution for dichotomous data). If assumptions of the model are violated, appropriate transformations will be performed (e.g. log, square root, rank) in order to satisfy the assumptions. Models supporting the primary analysis will include variables that may be associated with adverse neurodevelopment as covariates, (e.g., maternal education, history of prematurity or early term birth, number of open heart surgeries, number of cardiac catheterizations, number of serious adverse events, etc.). We will perform separate analyses for each potential covariate that include the variable, along with the matching factors and SES, and consider those variables associated with endpoint at a p -value <0.1 as covariates in stepwise generalized linear models. Collinearity will be assessed. The primary analyses and all secondary analyses will be conducted at the two-sided 5% level of significance. No multiple testing adjustments will be used for the secondary outcomes, although it is recognized that results of these tests should be interpreted with caution. Exploratory analyses of effect modification by neuro-resiliency polymorphisms may be performed by including interaction terms in the models.

MRI Outcomes:

MRI outcomes will include measures based on voxel-level analyses (e.g. grey matter volumes, regional cortical thickness, etc.) and outcomes that are summarized at the patient level (e.g. mean global FA). For unadjusted voxel-level analyses, two-sample t-tests (with appropriate transformations, if needed to satisfy the assumptions of the analyses) or Wilcoxon Ranks sum tests will be conducted to identify voxels that are significantly different between the two groups. P-value adjustments for multiple testing will be done to control the false discovery rate at 5% for voxel-level analyses for each MRI measure.

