16 CONFLICT OF INTEREST POLICY

The independence of this study from any actual or perceived influence is critical. Therefore any actual conflict of interest of persons who have a role in the design, conduct, analysis, publication, or any aspect of the trial will be disclosed and managed. Furthermore, persons who have a perceived conflict of interest will be required to have such conflicts managed in a way that is appropriate to their participation in this trial. The study leadership in conjunction with the NIH has established policies and procedures for all study group members to disclose all conflicts of interest and will establish a mechanism for the management of all reported dualities of interest. It is the responsibility of the Investigator to disclose all perceived conflicts of Interest to the study leadership.

17 APPENDIX A – DESCRIPTION OF TESTS OF NEURODEVELOPMENT, BEHAVIOR, AND QUALITY OF LIFE

ADOS-2: The Autism Diagnostic Observation Schedule- Second Edition (ADOS-2)⁶⁸ is a test which allows for accurate assessment and diagnosis of autism spectrum disorders across age, developmental level, and language skills. The test modules used will be 1-4 Cutoff scores are provided. There is no mean or standard deviation. Comparison scores can be used as a continuous variable (1- 10) since you cannot compare raw scores across modules.

Cut off scores are as follows.

- Module 1: few to no words autism cut off is 16. Some words autism cutoff score is 12
- Module 2: Younger than 5 years, autism cut off score is 10. Aged 5 and older autism cut-off score is 9
- Module 3: cutoff is 9
- Module 4: Autism cutoff score for Communication + Social Interaction is 10.

BASC-3: The Behavior Assessment System for Children-Third Edition (BASC-3)⁷³ is a parent, teacher, and self-report questionnaire. The BASC-3 measures emotional and behavioral functioning. It gives a multidimensional measure of a child's behavior both at home and at school. The BASC-3 is usually reported in T-scores, with a mean of 50 and a standard deviation of 10.

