Quality of Life Scale (QOLS): The QOLS is a 16-item self-report form that assesses overall quality of life on a scale of 16-112 (higher scores indicate better quality of life).^{81,82} The QOLS has high test-retest reliability, strong content validity, and good convergent and divergent construct validity. Scores have been validated in populations of healthy individuals (mean=90) and a number of disease specific groups.⁸¹ The total score is our main endpoint. The Linear Analog Scale is a self-report tool for assessing global QOL.⁸³ The scale is a vertical, 10-centimeter line with graded increments from 0-100 (higher scores indicating better QOL).⁸⁴ Linear analog scales have shown good validity and reliability in previous studies of adults with CHD.⁸⁴

Reading the Mind in the Eyes Task⁶⁹: This task measures general social intelligence and the ability to read and understand facial expression. Both the child and adult version will be administered. The mean for adults (\geq age 18 years) is 26.2 (SD 3.6).

Social Responsiveness Scale (SRS-2): The Social Responsiveness Scale- Second Edition (SRS-2)⁷¹ is a parent administered questionnaire. It measures interpersonal behavior, communication, and repetitive/stereotypic behavior characteristic of autism spectrum disorders (ASD). The SRS-2 is normed from ages 2.5 years through adulthood. The SRS scale is measured via T-score. A cut off T score of 76 or higher indicates a clinical diagnosis of autism. T scores of 66-75 indicate moderate deficiencies. T scores of 60-65 are mild deficits. A T score of 59 or lower indicates functioning that is age appropriate.

Vineland-III Questionnaire: The Vineland Adaptive Behavior Scales⁷⁰ measures the adaptive functioning of subjects, which generally refers to level at which they perform their activities of daily living. There are three indices – Communication, Daily Living, and Socialization. This measure is a parent report form. The mean is 100 and the standard deviation is 15.

VMI-6: The Beery Visual Motor Integration Test – 6th Edition (VMI-6)⁶⁶ measures the extent to which individuals can integrate their visual and motor abilities. It is commonly used to identify subjects who are having significant difficulty with visual-motor integration. The test is normed for ages 2- adult. The mean is 100 and the standard deviation is 15.

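### The ADOS-2 is compared only among subjects selected on an autism screen that the mutation may itself shift, which attenuates any carrier versus non-carrier difference

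*Protocol*

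**What the plan says.** - **Who is tested.** The footnote to Table 5 (Protocol 7.1.1.1): "The ADOS-2 will be administered if the SRS-2 Total Score ≥ 60 or if the coordinator, in his or her best judgment", after consulting the site psychologist, sees a strong likelihood of autism despite a lower score. The site investigator confirms such an override.
- **How the endpoint is defined.** Protocol 4.1.2 lists the ADOS-2 under its own lead-in: "Secondary neurodevelopmental outcomes for probands assessed for autism include the following".
- **How it is analysed.** Protocol 10.2.1 counts autism tests among the secondary outcomes and states: "The primary analysis for all endpoints (primary and secondary) will compare patients with and without known deleterious mutations". It does not say how untested subjects enter the ADOS-2 comparison.
- **The scale.** Appendix A gives module cut-offs and adds: "Comparison scores can be used as a continuous variable (1- 10").
- **The aim and hypothesis.** Aim 1 compares the groups on "social cognition and symptoms of autism spectrum disorder, and quality of life". Section 10.1 states: "We hypothesize that patients with deleterious mutations will have more neurodevelopmental abnormalities than CHD patients without these mutations".
- **The screen.** The SRS-2 is requested for every participant. "For participants <18 years of age, parent/caregiver will complete the SRS-2 School-age form", and a relative or caregiver is asked to complete the adult form for those aged 18 or more. On the threshold, Appendix A says: "T scores of 60-65 are mild deficits", so 60 is the lower edge of mild deficit.

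**The concern.** The gate is a symptom score of the kind the mutation is expected to worsen. If carriers have more autistic traits, more of them cross the threshold, and those extra entrants sit nearer the threshold than a typical control who crosses it. Inside the gate the two groups are therefore more alike than in the full cohort. Adjusting for site, CHD type, sex, age category and socioeconomic status does not undo this, because the selection acts through an outcome and not through a baseline factor.

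The assessed-only contrast answers a narrower question: how severe are ADOS-2 findings among those who screened positive? A null result could be misread as evidence that mutations have no bearing on autism. The coordinator override adds a subjective route in. Section 5.3 blinds site staff only as far as possible, and section 10.4.1 says the study involves no masking.

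**Working it through.** **The plan's own figure.** The protocol gives no sample size for the ADOS-2. The nearest is the section 10.3 table for any continuous outcome. A two-sample t-test at two-sided 5% and 80% power needs 175.4, 99.1 and 63.8 per group for 0.3, 0.4 and 0.5 SD, that is 176, 100 and 64 as stated. With 176 and 175 the power at 0.3 SD is 80.0%. Those figures reproduce, but they presume that everyone is measured.

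**Assumptions, none from the protocol.** A latent trait is shifted by δ = 0.5 SD in carriers. SRS-2 and ADOS-2 both load on it, with within-group correlation r. The SRS-2 has SD 10 and a control mean of 50 or 55. No override is modelled.

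**Formula.** On unit-SD scales both measures shift by s = δ√r. The gate is at c = (60 − control mean)/10, so c = 1.0 or 0.5. With λ(x) = φ(x)/[1 − Φ(x)]:

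- difference if all were tested: s
- difference among the assessed: s + r[λ(c − s) − λ(c)]

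| Control mean | r | s (all tested) | λ(c) | λ(c − s) | Assessed only | Kept |
|---|---|---|---|---|---|---|
| 55 | 0.4 | 0.316 | 1.141 | 0.918 | 0.227 | 72% |
| 55 | 0.6 | 0.387 | 1.141 | 0.871 | 0.225 | 58% |
| 55 | 0.8 | 0.447 | 1.141 | 0.832 | 0.200 | 45% |
| 50 | 0.4 | 0.316 | 1.525 | 1.278 | 0.217 | 69% |
| 50 | 0.6 | 0.387 | 1.525 | 1.225 | 0.207 | 53% |
| 50 | 0.8 | 0.447 | 1.525 | 1.180 | 0.171 | 38% |

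The loss is 28-62%. With δ = 0.3 the share kept is 37-71%.

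**Other model forms.** If the mutation shifts both scales by the same d (0.3 or 0.5 SD), the share kept is 1 + r[λ(c − d) − λ(c)]/d, which is 30-79% for r from 0.3 to 0.9. If the whole ADOS-2 effect runs through the SRS-2 score (control mean 50), it is 1 + [λ(c − d) − λ(c)]/d, about 22-23%. Attenuation appears in every case; its size depends on the model.

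**Binary version** (control mean 55, r = 0.6, δ = 0.5; assumed ADOS-2 cut at 1.5 SD). The screen admits 30.9% of controls and 45.5% of carriers.

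| Definition | Controls | Carriers | Odds ratio |
|---|---|---|---|
| All tested | 6.68% | 13.29% | 2.14 |
| Assessed only | 17.04% | 24.72% | 1.60 |
| All, screen-negatives counted negative | 5.26% | 11.25% | 2.28 |

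With 180 per group (the section 5.3 recruitment estimate), about 56 controls and 82 carriers would be assessed. Two-proportion power is about 18% assessed-only and about 54% for the two-stage definition.

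**What the screen misses.** In this base case it misses 1 − 5.26/6.68 = 21% of control positives and 1 − 11.25/13.29 = 15% of carrier positives. Over control means 50 and 55, δ of 0.3 and 0.5, and r of 0.4, 0.6 and 0.8, the miss rate runs from about 4% to 60% and is always higher in controls. That is why the two-stage odds ratio (2.28) exceeds the all-tested one (2.14). At r = 0.4 and mean 50 the gap is 2.23 against 1.87.

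**The ungated measure.** The SRS-2 shift in the base case is 0.387 SD. With 180 per group, power is Φ(0.387 × √90 − 1.96) = Φ(1.71), about 96%.

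**The case against.** Three points carry weight.

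1. **An ungated autism comparison already exists.** Section 10.2.1 lists the instruments reported by parents and teachers as secondary outcomes, and the SRS-2 is one. A reader might infer that the protocol has no whole-cohort autism comparison. It does; section 4.1.2 simply does not name it. This limits the harm, but the ADOS-2 contrast as defined is still attenuated.
2. **The analysis set is partly inferred.** Section 10.2.1 allows a logit model and Appendix A gives cut-offs, so a whole-cohort binary ADOS-2 outcome is not ruled out, and an unseen statistical analysis plan may specify one. Against that, section 4.1.2 defines the outcome only for those assessed, and a plan that follows it inherits the problem.
3. **Counting screen-negatives as negative has its own bias.** The misses are not few and differ by group, so the odds ratio can move away from the null. Part of the gain in power is the SRS-2 difference re-entering through the denominator. This stands, and the fix has to carry it.

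Two-stage testing to limit burden (about 3.5 hours without autism testing, 4.5 with) is reasonable. The defect lies in what is compared, not in the testing rule.

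**Conclusion.** The concern holds for one secondary outcome. Read together, the Table 5 footnote, section 4.1.2 and section 10.2.1 compare carriers with non-carriers inside a group selected on a trait the mutation is hypothesised to raise. The result is biased toward no difference: roughly 30-60% of the ADOS-2 difference is lost for correlations of 0.4 to 0.8, a control SRS-2 mean of 50 to 55 and a 0.5 SD latent shift. These inputs are assumptions and the override is not modelled, so the direction is firmer than the size.

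A reader might go further and infer that the design hides most of any autism difference, or that carriers and non-carriers would look the same once tested. The documents do not support that. They give no SRS-2 distribution or SRS-2/ADOS-2 correlation, and in the base case 58% of the difference survives, with an odds ratio of 1.60. More than half is lost only at high correlation or when the effect runs wholly through the screened trait. The WRAT-4 primary outcome is unaffected. The wording should be corrected, but the study's main conclusion does not depend on it.

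**What to change.** Amend sections 4.1.2 and 10.2.1:

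1. Name the SRS-2 T-score in all participants as the main between-group comparison of autistic traits.
2. Define the ADOS-2 endpoint as screen-positive (by score or override) and ADOS-2 above the module cut-off stated in Appendix A, over all participants with an SRS-2, analysed by logistic regression with the planned adjustment factors.
3. Report ADOS-2 comparison scores among those assessed as descriptive only.
4. Add a sensitivity analysis that varies the share of ADOS-2 positives missed by the screen, separately by group. Flag override-triggered tests and repeat the analysis without them.

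**Cost.** Wording and analysis only; no extra testing and no change to who is tested. The downside is that screen false negatives are counted as negative, may differ between groups and can push the odds ratio away from the null. The endpoint should therefore be labelled two-stage positivity and not autism prevalence.
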